9.3 Analysis Plan

Descriptive analysis will explore the acceptability of group MCT by examining the number of eligible participants who took up the offer of intervention and the retention rate. Analysis will test treatment effects across time (baseline, post-treatment, and 6-month follow-up) using repeated measure analysis of variance. Main effects will be followed by Bonferroni corrected pairwise comparisons for each outcome. Within-group effect size (Hedges' g) will be calculated for ITT and completer samples and will be used to estimate the required sample size for a full randomised trial. Clinical significance of treatment effects will be assessed using the Jacobson method [39] to establish whether participants could be considered recovered as a result of treatment. This method allocates each patient to one of four possible outcomes: (1) reliable deterioration; (2) no change; (3) reliable improvement; and (4) recovered. The first three outcomes are derived solely from a reliable change index (RCI) which compares treatment outcomes to normative data from non-clinical samples to determine whether the magnitude of change is statistically significant. To be classified as 'recovered', patients need to demonstrate both a reliable change and a score that falls below the established clinical cut-off. Therefore patients will be classified as 'recovered' where post-treatment HADS total <13, RCI will be 8 based on normative data from a large non-clinical sample [40].

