Objectives:	
 1. To obtain evidence of potential efficacy of group MCT in alleviating emotional distress in cancer survivors. 2. To assess the acceptability of the intervention to patients. 3. To obtain data to inform sample size calculations for a subsequent Phase II trial 4. Determine whether group MCT for cancer survivors can be easily delivered in routine clinical practice
Measures:	
Primary endpoint: Severity of depression and/or anxiety symptoms at post-treatment, and at 3 and 6 months follow-up, measured by the full scale score on the Hospital Anxiety and Depression Scale (HADS; [33]).
 
Secondary endpoints: Cognitive Attentional Syndrome-1 [19]; Fear of Cancer Recurrence Inventory [35]; Impact of Events Scale-Revised (IES-R) [36]; Metacognitions Questionnaire-30 (MCQ-30) [37]; Functional Assessment of Cancer Therapy-General (FACT-G) [38].

Population:	Patients who are referred to the Clinical Health Psychology Service experiencing clinically significant distress, operationally defined as a score of ≥ 15 on the full scale score on the HADS [32].
Intervention:	The intervention will constitute 6 sessions of group MCT. Clinical psychologists trained in group MCT will deliver the therapy to groups of 4-8 patients referred to the Liverpool psycho-oncology service, who meet study criteria and consent to participate.
Study duration:	15 months maximum

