6. STUDY DESIGN

6.1. Design

An open trial (single arm, single site) with follow-up at 3 and 6 months.

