6.2. Study Measures

All outcome measures will be administered pre-treatment, post treatment and at 3- and 6-months follow-up.

(i) Primary outcome:

Hospital Anxiety Depression Scale (HADS) [32] total was chosen because: 1) it has proven construct validity for measuring emotional distress in cancer patients [33], and 2) it is the optimal measure of general distress for evaluating treatment efficacy in heterogeneous cancer populations [34].

(ii) Secondary outcomes:

Cognitive Attentional Syndrome-1 [19] will assess rumination and worry. A single measure rather than separate measures of rumination and worry will reduce patient burden.

Fear of Cancer Recurrence Inventory [35] will assess fear of recurrence

Impact of Events Scale-Revised (IES-R) [36] will assess trauma related symptoms.

Metacognitions Questionnaire-30 (MCQ-30) [37] will assess metacognitive beliefs.

Functional Assessment of Cancer Therapy-General (FACT-G) [38], will assess cancer-specific quality of life.

(iii) Sample characteristics and potential covariates: We will record socio-demographic characteristics, time and nature of cancer diagnosis, psychiatric history, and previous and current treatment including any psychotropic medication.

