9. STATISTICS AND DATA ANALYSIS

9.1. Sample size and feasibility

The study will require 40 patients to be recruited, allowing for attrition of 33% from baseline to 6-month follow-up to leave a sample of 27 (see power calculation). The CHPS receives approximately 400 new referrals annually. In a recently completed open trial of MCT hosted within the CHPS, approximately half of all referrals fulfilled eligibility criteria. Approximately 50% of eligible patients declined to participate. If we assume a more conservative 25% take-up, this will provide 50 patients, i.e. 25% more than needed.

To date, we have completed two MCT training groups. To determine the feasibility of the proposed study, we followed the methodology outlined above. Six out of nine patients (i.e. 66%) were considered treatment completers (i.e. they attended the first and last sessions, and at least two of the four interim sessions offered to them). Reasons for non-completion included disengagement ($n = 1$), work commitments ($n = 1$) and change in personal circumstances ($n = 1$). These preliminary data indicate that the proposed attrition rate outlined above is feasible for this patient group.

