9.2 Power calculation

The primary indicator of efficacy will be change in HADS total between pre-treatment and 6-months follow up. In a recently completed open trial of MCT, the estimated between-patient standard deviation was approximately 7. As this is based on a small number of patients (n=20), a between-patient standard deviation of 12 will be used. No information on within-patient standard deviation is available so the between-patient standard deviation is used as a conservative measure. A trial with 95% power to detect a reduction in HADS score of 8 points, which is the minimum reliable difference we seek to obtain between baseline and 6 months follow up, requires 24 patients (one-sided alpha = 0.01). To account for clustering by group we will increase the sample size by a factor of 1.10 (1+ (average cluster size-1)) x intra-class correlation coefficient), therefore the required sample size will be 27.

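### Section 9.3 tests three of the four scheduled visits, leaving out 3 months, with an ANOVA that drops patients with a missing listed visit unless values are imputed

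*Protocol*

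**What the plan says.** Four places in the protocol name visits for the HADS.

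- Section 2 (Study Summary, Measures) defines the primary endpoint as "Severity of depression and/or anxiety symptoms at post-treatment, and at 3 and 6 months follow-up".
- Section 6.1 describes the design as "An open trial (single arm, single site) with follow-up at 3 and 6 months", and section 6.2 adds: "All outcome measures will be administered pre-treatment, post treatment and at 3- and 6-months follow-up".
- Section 9.2 narrows the target: "The primary indicator of efficacy will be change in HADS total between pre-treatment and 6-months follow up".
- Section 9.3 then says: "Analysis will test treatment effects across time (baseline, post-treatment, and 6-month follow-up) using repeated measure analysis of variance". Bonferroni-corrected pairwise comparisons follow for each outcome. Hedges' g is to be computed in ITT and completer samples and used to size a later randomised trial.

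On losses, section 9.1 recruits 40, "allowing for attrition of 33% from baseline to 6-month follow-up to leave a sample of 27". It supports that rate with two training groups: "Six out of nine patients (i.e. 66%) were considered treatment completers".

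**The concern.** There are two linked problems.

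First, the bracketed list of visits in 9.3 is closed and leaves out 3 months. No other section analyses the 3-month scores. One component of the stated primary endpoint, and the 3-month value of every secondary outcome, is collected without a planned test.

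Second, 9.3 fixes a method that copes badly with the attrition the protocol itself expects. A classical repeated-measures ANOVA discards a patient who lacks any listed visit, together with the scores that patient did give. The trial has one arm, so no control group shares any distortion from selective loss; it goes straight into the estimated change. Because ITT is attached only to the effect size, the significance test and the Hedges' g that is to size the next trial (objective 3 in section 5) may describe different patients.

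**Working it through.** **1. Visits side by side**

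| Place | Baseline | Post-treatment | 3 months | 6 months |
|---|---|---|---|---|
| Section 2, primary endpoint | – | yes | yes | yes |
| Section 6.2, collected | yes | yes | yes | yes |
| Section 9.2, primary indicator | yes | – | – | yes |
| Section 9.3, tested | yes | yes | **no** | yes |

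The 9.2 contrast lies inside the 9.3 list; the 3-month component of section 2 does not.

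**2. Patients entering the ANOVA without imputation**

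The plan's own steps: 24 × 1.10 = 26.4, rounded up to 27; and 40 × (1 − 0.33) = 26.8, about 27. Both agree with the protocol. (The 24 itself does not follow from 9.2's inputs: [12 × (2.326 + 1.645) / 8]² = 35.5. That is a separate matter, and nothing here depends on it.)

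So at most about 27 enter the test and about 40 − 27 = 13 do not. The 33% refers to 6 months, so anyone seen then who missed post-treatment is lost as well. If a share r has a post-treatment score, complete cases lie between 40 × (0.67 + r − 1) and 40 × min(0.67, r). For r = 0.80 this is 18.8 to 26.8; for r = 0.95, 24.8 to 26.8. The protocol gives no r; 0.80–0.95 is assumed.

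**3. Size of a possible bias**

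Taken from 9.2: SD 7 (recent open trial) and SD 12 (planning value), used as the SD of change as 9.2 does, and the 8-point target. Assumed: equal visit variances; baseline correlated 0.5 with later visits; early and 6-month change correlated 0.5–0.7; mean loss 13/40, with the odds of loss multiplied by 1, 1.5 or 3 per SD less early improvement. Simulated, 40 patients per trial:

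| Odds ratio, correlation | Complete-case bias, SD 7 | Complete-case bias, SD 12 | True null rejected, one-sided 0.01 | Same, at 0.01/3 |
|---|---|---|---|---|
| 1 (unrelated loss) | about 0 | about 0 | about 1% | about 0.3% |
| 1.5, 0.5 | −0.4 to −0.5 | −0.8 | about 2% | about 0.8% |
| 3, 0.7 | −1.4 | −2.4 to −2.5 | about 10% | about 4.4% |

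A negative sign means too favourable. Against 8 points, 0.4/8 = 5% and 1.4/8 = 18% at SD 7; 0.8/8 = 10% and 2.5/8 = 31% at SD 12. The rejection rates are for a paired t-test of baseline to 6 months. The 0.01/3 column allows for the three pairs among three visits.

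**4. What a mixed model recovers under the same assumptions**

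| Dropouts with a post-treatment score | Bias, SD 7 | Bias, SD 12 |
|---|---|---|
| all | about 0 | about 0 |
| half | −0.1 to −0.4 | −0.1 to −0.6 |
| none (no post-baseline score) | −0.2 to −1.0 | −0.4 to −1.6 |

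**5. Precision when loss is unrelated to response**

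At SD 12, 8 points and one-sided 0.01, the noncentral t with n = 27 gives power 0.83 for complete cases. The simulated mixed model reaches about 0.86–0.90.

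**The case against.** The best defence is that the second problem is conditional. The protocol nowhere says that only complete cases are analysed, its mention of ITT shows that some handling of dropouts is intended, and imputation rules commonly sit in a statistical analysis plan, which is not shown here. This stands as far as it goes: the lack of an imputation rule is not the point. What the protocol does fix is a method that needs complete data or imputation, alongside a planned one-third loss.

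The bias figures also rest on assumptions. No section supports the odds ratios or correlations. Of the three non-completers in 9.1, one disengaged; the other two left for work or a change in personal circumstances, which on their face are not response-related. The figures are illustrations, not predictions.

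A reader might infer more than the protocol supports in four ways:

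- *That the main efficacy question goes untested.* It does not: 9.3 includes baseline and 6 months.
- *That the test falls short of its planned size.* The 27 already allows for the expected attrition; the count drops below it only if some patients seen at 6 months missed post-treatment.
- *That the planned procedure has a 10% false-positive rate.* That figure is the upper end for one uncorrected paired test. Section 9.3 plans Bonferroni-corrected comparisons and states no alpha.
- *That leaving therapy group out of 9.3, after 9.2 inflates for it, undermines the test.* The factor 1.10 implies an ICC of 0.10/(m − 1), or 0.033, 0.020 and 0.014 for groups of 4, 6 and 8. At 0.020 a one-sided 0.01 test runs near 0.013, and only if change, not just level, clusters by group.

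**Conclusion.** The point holds in two parts. The omission of 3 months from 9.3 is a contradiction on the face of the protocol and needs no assumption. It affects the 3-month part of the primary endpoint and of all secondary outcomes, but not the primary indicator in 9.2.

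The ANOVA is a poor choice for the attrition expected: absent imputation, about 13 or more of 40 patients leave the test along with any partial data. If loss is unrelated to response, the cost is precision alone. If loss follows poor early response, the apparent improvement is overstated by an amount that could matter against an 8-point target, and the test may disagree with the ITT effect size. Whether that happens cannot be told from the protocol. The defect is worth correcting before analysis, and it is not fatal to the trial.

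**What to change.** Replace the ANOVA sentence in 9.3 with wording such as:

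> HADS total at baseline, post-treatment, 3 and 6 months will be analysed with a linear mixed model (REML) using all available scores from every patient with a baseline score. Visit is a fixed effect, the within-patient covariance is unstructured, and degrees of freedom are Kenward-Roger. The single primary contrast is baseline to 6 months at one-sided 0.01. Baseline to post-treatment and baseline to 3 months are supporting contrasts with Bonferroni correction. Secondary outcomes use the same model.

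Then:

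- Limit the existing Bonferroni sentence to the supporting contrasts. All pairs of four visits would be 6 instead of the present 3.
- Amend the primary endpoint in section 2 to say that 6 months is primary and the other visits supporting. This changes the stated endpoint and should be declared as such. Sections 6.2 and 9.2 can stay as they are.
- State that the ITT Hedges' g uses the same patients as the model.
- Optionally, add a sensitivity analysis of baseline-to-6-month change with a therapy-group random effect, reporting the ICC of change for the next trial. It should not be the primary test.

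The cost is new wording and slightly more analysis; the 3-month scores are already collected. The model estimates 10 covariance parameters from 40 patients. In simulation with unrelated loss its one-sided 0.01 test ran at 0.008–0.012, but with completers-minus-1 degrees of freedom standing in for Kenward-Roger, so that is indicative only. Bias remains where dropouts give no score after baseline, and no change of model removes it.

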10. ETHICAL AND REGULATORY REQUIREMENTS

10.1. Ethical Approval

This study will be subject to NHS Research Ethics Approval and Health Research Authority (HRA) approval. The study will be submitted to the Royal Liverpool and Broadgreen University Hospital for Confirmation of Capacity and Capability. This study will not be initiated before the protocol, informed consent forms and participant information sheets have received approval/ favourable Research Ethics Approval and HRA approval. Should a protocol amendment be made that requires Research Ethics Committee (REC) approval, the changes in the protocol will not be implemented until the amendment and revised informed consent forms and participant and (if appropriate) have been reviewed and received favourable REC and HRA opinion. The Chief Investigator will have a copy of the HRA approval letter before accepting participants into the study. The study will be conducted in accordance with the recommendations for physicians involved in research on human subjects adopted by the 18th World Medical Assembly, Helsinki 1964 and later revisions.

10.2. Sponsorship and Indemnity

The University of Liverpool will act as Sponsor for this study. Delegated responsibilities will be assigned to the Royal Liverpool and Broadgreen NHS Trust which is taking part in this study. The University of Liverpool holds indemnity and insurance cover with Marsh UK LTD, which apply to this study.

10.3. Participant Information and Informed Consent

The patient's consent to participate in the study will be obtained after a full explanation of the study has been given and the patient has been given sufficient time to discuss participation in the study with friends and family. A contact number will be given to the patient should they wish to discuss any aspect of the study.

The right of the patient to refuse to participate in the study without giving reasons must be respected. Similarly, the patient must remain free to withdraw at any time from the protocol treatment without giving reasons and without prejudicing his/her further treatment.

10.4. Participant Confidentiality and Data Protection

All information collected during this study will be kept confidential in accordance with NHS Data Protection guidelines. Identifying information will be anonymised. Confidentiality will only be breached if a participant discloses information which may indicate harm to themselves or others. We will take every opportunity to discuss any possible breaches of confidentiality patients prior to informing any appropriate agencies e.g. oncology staff, GP or A&E services.

Participants will be allocated a study identity code number by the study team for use on all study documents and the electronic database. The study team will make a separate confidential database for the participants name, date of birth and study identity code to permit identification of participants enrolled in the study e.g. for follow-up. All other information will be anonymised. All study documents (including participant's written consent forms) which are to be held at the participating centre will be held in strictest confidence.

Data will only be available through restricted, shared areas on the secure University of Liverpool computer systems (password and username secured). Participants will be informed of this on the participant information sheet and will be asked to consent to this at the time of consent to the study. All paper forms shall be filled in using black or blue ballpoint pen. Errors shall be lined out but not obliterated by using correction fluid and the correction inserted, initialled and dated.

All member of staff involved with the study must comply with the requirements of the Data Protection Act 1998 with regard to the collection, storage, processing and disclosure of personal information and will uphold the Act's core principles.

Statistical analysis will be directed and supervised by [name]. No information which may allow identification of individual participants will be included in publications or dissemination activities.

NHS patient data collected within RLBUHT will follow the standard operating procedure which states all information involving NHS patients, interventional or observational should be retained for a minimum of 10 years after completion of the study in a secure storage area with limited access. The University of Liverpool will arrange appropriate storage and archiving of data.

10.5. Protocol Amendments

Any changes in research activity will be reviewed and approved by the Chief Investigator (CI) and submitted in writing to the appropriate REC and local research site for approval prior to being included in an amended protocol.

10.6. Audit

The study may be subject to inspection and audit by the University of Liverpool under their remit as sponsor and other regulatory bodies to ensure adherence to GCP and the NHS Research Governance Framework for Health and Social Care (2nd edition).

10.7 Funding

This study is unfunded.

12. END OF STUDY

The study end date is deemed to be the date of the last data capture. The CI has the right at any time to terminate the study for clinical or administrative reasons. The end of the study will be reported to the REC within the required timeframe if the study is terminated prematurely. Investigators will inform patients of any premature termination of the study and ensure that the appropriate follow up is arranged for all involved. Following the end of the study a summary report of the study will be provided to the REC within the required timeframe

13. ARCHIVING

Documents will be stored by the University of Liverpool and at CHPS in a way that will facilitate the management of the study, audit and inspection. Study documentation will be securely stored and retained for a period of 10 years for possible audit or inspection. Access to these documents will be restricted to authorised persons.

14. PUBLICATION POLICY

The main findings will be published in open-access journals and secondary data will be reported in other peer reviewed journals.

